2.4.5.4 Analyses of vital sign variables

The summary statistics (including number, mean, median, Q1, Q3, standard deviation, minimum and maximum) of all vital signs variables (values and changes from baseline) will be calculated for each visit or study assessment (baseline, each postbaseline time point, last on-treatment and/or worst on-treatment value) by treatment group. For all the parameters, mean changes from baseline with the corresponding standard error will be plotted over time (at same time points) in each treatment group.

The incidence of PCSAs at any time during the treatment-emergent adverse event period will be summarized by treatment group irrespective of the baseline level and/or according to the following baseline status categories:

- Normal/missing
- Abnormal according to PCSA criterion or criteria

2.4.5.5 Analyses of electrocardiogram variables

The summary statistics (including number, mean, median, Q1, Q3, standard deviation, minimum and maximum) of all ECG variables (central laboratory values and changes from baseline) will be calculated for each visit or study assessment (baseline, each postbaseline time point, last on-treatment and/or worst on-treatment value) by treatment group. For all the parameters, mean changes from baseline with the corresponding standard error will be plotted over time (at the same time points) in each treatment group.

The incidence of PCSAs at any time during the treatment-emergent adverse event period will be summarized by treatment group irrespective of the baseline level and/or according to the following baseline status categories:

- Normal/missing
- Abnormal according to PCSA criterion or criteria

2.4.6 Analyses of pharmacokinetic and pharmacodynamics variables

2.4.6.1 Pharmacokinetic analysis

2.4.6.1.1 Analyses of serum concentrations of dupilumab

Serum concentrations of dupilumab will be summarized in the PK population using arithmetic and geometric means, SD, standard error of the mean, coefficient of variation, minimum, median and maximum by visit. If date and/or time of the drug injection and/or sampling is missing then the concentration will not be taken into account. For dupilumab-treated patients, where concentration values are below the lower limit of quantification (LLOQ), one-half of the LLOQ will be used. Values will be expressed in the tables with no more than three significant figures. For patients not treated by dupilumab, concentration values below the LLOQ will be taken into account with a plasma concentration considered equal to 0.

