9.2.5 Systemic drug concentration and anti-drug antibodies

9.2.5.1 Sampling time

Blood samples of serum functional dupilumab and anti-dupilumab antibodies will be collected as designated in the study flow chart (Section 1.1). Patients who discontinue early from treatment or patients who choose not to roll over into a long-term study may be asked to return to the clinic to have additional ADA samples collected for analysis based on the overall clinical presentation at that time.

In the event of an SAE or any AESI of anaphylaxis or systemic allergic reaction related to IMP and requiring treatment, or severe injection site reaction lasting longer than 24 hours, samples will be collected near the onset and resolution of the event for any additional analysis if required or for archival purposes. An unscheduled systemic drug concentration page in the e-CRF must be completed as well.

Pre-existing anti-drug antibodies are defined as:

- An ADA positive response in the assay at baseline with all post treatment ADA results negative, OR
- An ADA positive response at baseline with all post treatment ADA responses less than 4-fold over baseline titer levels.

Treatment-emergent anti-drug antibodies are defined as:

- An ADA positive response in the assay post first dose, when baseline results are negative or missing.
- Treatment-boosted anti-drug antibodies are defined as:
- An ADA positive response in the assay post first dose that is greater-than or equal to 4-fold over baseline titer levels, when baseline results are positive.

Treatment-emergent (TE) ADA responses are further classified as Transient, Persistent or Indeterminate

- Persistent Response- defined as a treatment-emergent response with two or more consecutive ADA positive sampling time points, separated by more than 12-week period (with no ADA negative samples in between).
- Indeterminate Response- defined as a treatment-emergent response with only the last collected sample positive in the ADA assay
- Transient Response defined as a treatment-emergent response that is not considered persistent OR indeterminate

Unused samples collected for drug concentration or ADA analyses may be used for exploratory analyses.

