10.3.4 Handling of patients after permanent treatment discontinuation

Patients will be followed-up according to the study procedures as specified in this protocol up to the scheduled date of study completion, or up to recovery or stabilization of any AE to be followed-up as specified in this protocol, whichever comes last. Study investigators should continue OCS dose adjustment after treatment discontinuation, as guided by their medical judgment, including up-titration and down-titration in accordance with Table 2 (Titration schedule for oral corticosteroids during the OCS Reduction Phase of the Randomized Period).

All cases of permanent treatment discontinuation should be recorded by the Investigator in the appropriate pages of the CRF when considered as confirmed.

Patients who discontinue early from treatment may be asked to return to the clinic to have additional ADA samples collected based on the overall assessment of antibody titers and clinical presentation.

Patients who permanently discontinue the study medication will be asked and encouraged to return to the clinic for remaining study visits and participate in follow-up assessments according to the visit schedule.

Under exceptional circumstances when a patient cannot come to the site for the scheduled visit/s, a phone contact can be made after sponsor approval is given. During the phone contact information about AEs, concomitant medications and exacerbation events should be collected.

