2.1.5 Pharmacokinetic variables

Blood samples of serum functional dupilumab will be collected at Visit 3 (Week 0) as sample before the first dose, at Visits 5 (Week 4), 7 (Week 8), 8 (Week 12), 11 (Week 24) as trough samples prior to IMP dosing at each visit, and at Visit 14 (Week 36) during the follow up period.

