2.3.3 Pharmacokinetics population

The PK population will consist of all patients in the safety population with at least 1 evaluable functional dupilumab concentration result. Patients will be analyzed according to the treatment they actually received.

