1-: up to min(1st dose date/time, end of randomization date); 1+: after min(1st dose date/time, end of randomization date).

For the pharmacokinetics/pharmacodynamics variables summary, the reference date for the derivation of relative days of measurements will be the date of first IMP administration if the patient is treated with study treatment, or the randomization date if the patient is not treated. Pharmacokinetics /pharmacodynamics variables will be summarized by the analysis window defined in Table 10 for the by visit descriptive analyses. All available values of measurements will be assigned to the appropriate visit window. In the event of multiple measurements of the same test in the same window, the one closest to the targeted visit date will be used for the by-visit summary. If they are at the same distance to the target day, the latest one will be used. For procedures planned on Visit 3, if it is done on the same date as the first IMP injection but the performance time is missing, it will belong to Visit 3 time window.

		Time windows for					
Visit	Target day	Blood eosinophil	Exhaled NO	Systemic drug concentration	Anti-drug antibodies	Eotaxin-3, total IgE, TARC Antigen- specific IgE, periostin	Sputum ILC2 and CD34 cells and sputum and blood cytokines
Visit 3 (Week 0)	1	<-1 ⁻	-14-1 ⁻	<-1 ⁻	1-	1-	1-
Visit 4 (Week 2)	15		1+-21				
Visit 5 (Week 4)	29	1+-42	22-35	1+-42		1+-56	
Visit 6 (Week 6)	43		36-49				
Visit 7 (Week 8)	57	43-70	50-70	43-70			
Visit 8 (Week 12)	85	71-98	71-98	71-126	1+-126	57-112	
Visit 9 (Week 16)	113	99-126	99-126				
Visit 10 (Week 20)	141	127-154	127-154			113-154	
Visit 11 (Week 24)	169	155-210	155-182	127-210	127-210	>154	1+-210
Visit 12 (Week 28)	197		183-210				
Visit 13 (Week 32)	225		211-238				
Visit 14 (Week 36)	253	>210	>238	>210	>210		>210
1-: up to 1 st dose date/time; 1+: after 1 st dose date/time;							

 Table 10 – Time window for pharmacokinetics/pharmacodynamics variables

For not treated but randomized patients: 1⁻: up to randomization date; 1⁺: after randomization date

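### The by-visit dupilumab concentration rows for Weeks 4 to 24 have no on-treatment condition, so values from patients who permanently stopped study drug are averaged with on-treatment troughs

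*SAP*

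**What the plan says.** SAP 2.1.5 schedules drug concentration samples at Week 0, at Weeks 4, 8, 12 and 24, and at Week 36. The Week 4 to 24 samples are taken "as trough samples prior to IMP dosing at each visit".

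SAP 2.4.6.1.1 sets out the summary: "Serum concentrations of dupilumab will be summarized in the PK population using arithmetic and geometric means", with SD, standard error, coefficient of variation, minimum, median and maximum, by visit. Its one sample-level exclusion is "If date and/or time of the drug injection and/or sampling is missing then the concentration will not be taken into account". For dupilumab-treated patients, a value below the lower limit of quantification (LLOQ) is replaced by half that limit. Protocol Table 4 gives the limit as 0.078 mg/L.

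SAP 2.3.3 defines the population by patient: "all patients in the safety population with at least 1 evaluable functional dupilumab concentration result". Evaluable is not defined.

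SAP 2.5.4 states: "All available values of measurements will be assigned to the appropriate visit window". In Table 10 the drug concentration windows are first dose to Day 42 (Week 4), Days 43-70 (Week 8), Days 71-126 (Week 12) and Days 127-210 (Week 24). Where a window holds several values, "In the event of multiple measurements of the same test in the same window, the one closest to the targeted visit date will be used".

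Protocol 10.3.4 states: "Patients who permanently discontinue the study medication will be asked and encouraged to return to the clinic for remaining study visits".

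**The concern.** None of these rules depends on whether the patient is still receiving drug. A patient who stops at Week 6 and attends Weeks 8, 12 and 24 as asked contributes three concentrations from a declining or washed-out profile. Each is averaged with the troughs of patients still being dosed.

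Systemic exposure is a stated secondary objective, and this table is the SAP's main summary of it. A reader will take the rows as exposure under the assigned regimen, since SAP 2.1.5 calls the samples troughs. With off-drug values included, they understate it.

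The plot of concentration by visit and ADA category (SAP 2.4.6.1.2) is more exposed. Some ADA categories may be small, and Protocol 10.3.3 requires permanent discontinuation after a treatment-related anaphylactic or systemic allergic reaction that needs treatment. If such reactions cluster in ADA-positive patients, low concentrations caused by stopping drug could be read as an effect of the antibodies.

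**Working it through.** **Do the rules let off-drug samples in?**

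1. The patient stays in the PK population, which needs only one evaluable result and has no on-treatment condition.
2. The visit still takes place (Protocol 10.3.4), and the flow chart schedules a PK sample at Weeks 4, 8, 12 and 24.
3. The missing-date rule does not remove the sample, because the last injection and the sampling time are both known. Nor can it be read as excluding any visit without an injection. The last planned dose is at Week 22, so that reading would delete every Week 24 and Week 36 sample.
4. The window rule assigns the sample by study day alone.
5. A result below the LLOQ becomes 0.078/2 = 0.039 mg/L.

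The SAP draws the distinction elsewhere. It plans on-treatment analyses for the primary and key secondary endpoints (2.4.4.1.3, 2.4.4.2.1.2) and limits worst safety values to the treatment epoch (2.4.5). The PK section has no equivalent.

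**How much could it matter?** The plan gives no PK figure to reproduce, so this is an illustration.

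- From the documents: LLOQ 0.078 mg/L; 90 randomized patients per group.
- Assumed: N = 85 dupilumab patients sampled at a visit; n = 2, 5 or 8 of them off drug; on-treatment geometric mean C = 20, 40 or 80 mg/L; off-drug value c of either 0.039 mg/L (all below the LLOQ, the worst case) or 0.05C.

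On the log scale the mixed mean is [(N − n) log C + n log c]/N, so mixed geometric mean ÷ on-treatment geometric mean = (c/C)^(n/N).

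| Off drug (n of 85) | C = 20, all below LLOQ | C = 40, all below LLOQ | C = 80, all below LLOQ | 5% of trough left |
|---|---|---|---|---|
| 2 | 0.863 | 0.849 | 0.836 | 0.05^(2/85) = 0.932 |
| 5 | 0.693 | 0.665 | 0.639 | 0.05^(5/85) = 0.838 |
| 8 | 0.556 | 0.521 | 0.488 | 0.05^(8/85) = 0.754 |

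For the arithmetic mean at n = 5, the ratio is about 80/85 = 0.941 when all five are below the LLOQ, and (80 + 5 × 0.05)/85 = 0.944 with 5% residual drug.

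For the median at n = 5, the middle of 85 values is rank 43. With the five lowest off drug, that is rank 38 of the 80 on-drug values, about 4% below their median if concentrations are log-normal with a CV of 50% (assumed).

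The exponent n/N also explains the ADA plot: one off-drug patient is a larger share of a small category than of the whole arm.

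**Would a 14 ± 3 day post-dose filter work?** The Week 22 dose falls on Day 155 ± 3 and the Week 24 visit on Day 169 ± 3. The interval is therefore 14 ± 6, or 8 to 20 days, for a fully compliant patient. A 14 ± 3 day limit (11 to 17 days) could drop valid samples.

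**The case against.** The strongest reply is that the SAP never labels the table as trough data. SAP 2.1.5 uses the word for how scheduled samples are drawn; SAP 2.4.6.1.1 speaks only of serum concentrations. The objective is systemic exposure, and summarizing everyone in the PK population is a legitimate reading of it. The same table reports the median, which barely moves, and the minimum, which would show a washed-out value openly. Nothing is tested, and population PK is planned in separate documents (Protocol 11.4.4.1). All of this stands and limits the consequence. It does not supply an on-treatment condition, and it leaves the geometric mean and the ADA plot open to misreading.

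A reader might also infer that the SAP keeps samples triggered by serious adverse events or adverse events of special interest (SAE/AESI). The documents do not establish that. Under Protocol 9.2.5.1 "samples will be collected near the onset and resolution of the event", but only for further analysis if needed or for archiving, and on an unscheduled eCRF page. SAP 2.5.5 admits unscheduled laboratory, vital sign and ECG values to by-visit summaries and does not mention PK. Set against the all-available-values rule in SAP 2.5.4, this is an ambiguity. It would also matter little. With visit days uniform over ±3 days and event days uniform over the window (both assumed), an event sample would displace an existing scheduled one in about 7% of cases at Week 4, 11% at Week 8, 5% at Week 12 and 4% at Week 24.

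It is also tempting to note that the Week 24 window ends 210 − 155 = 55 days after the last planned dose. Day 210 is only a window edge: the visit is due on Day 169 ± 3, no PK sample is scheduled at Week 28 or 32, and the value nearest Day 169 is used.

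**Conclusion.** The gap is real. Applied as written, the SAP puts concentrations from patients who permanently stopped study drug into the Week 4, 8, 12 and 24 rows and the ADA-category plot, with values below quantification set to 0.039 mg/L. The expected direction is downward and the geometric mean is most sensitive. In the 5-of-85 illustration it falls to 64-69% of the on-treatment value at worst and 84% with 5% of trough remaining, against about 94% for the arithmetic mean.

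The true size cannot be worked out. The documents give no trough level, discontinuation rate or washout rate, and the worst case needs every off-drug value to be below the LLOQ. To conclude that the Week 4 to 24 means are not trough exposure at all would go too far. Most values should be scheduled pre-dose samples from continuing patients, mixed with an unknown off-drug share. The primary efficacy analysis and the multiplicity procedure are unaffected. The change is still worth making because it is cheap and protects a secondary objective.

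**What to change.** Amend SAP 2.4.6.1.1 and the ADA-PK paragraph of 2.4.6.1.2 before database lock:

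- Base the Week 4, 8, 12 and 24 rows and the ADA-category plot on scheduled samples from patients who had not permanently discontinued study drug before that visit, using a flag derived from dosing dates. Keep patients with a temporary interruption, whose lower exposure is real.
- Do not use a 14 ± 3 day post-dose filter. Protocol 8.1.4 sets that interval between doses, and the filter could drop compliant Week 24 samples.
- List or summarize post-discontinuation concentrations separately by time since last dose, and keep Week 36 as its own washout row.
- State that unscheduled PK samples triggered by an SAE or AESI are not used in the by-visit summary, and reconcile 2.5.4 with 2.5.5 on this.

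The cost is a few sentences, one derived flag and slightly fewer samples per row. All samples remain available to the population PK analysis.

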2.4.6.1.2 Analyses of ADA variables

The following summary will be provided based on ADA population:

- Number (%) of patients negative in ADA assay at all time points analyzed
- Number (%) of patients positive in ADA assay at any time points analyzed
- Number (%) of patients with pre-existing immunoreactivity
- Number (%) of patients with treatment-emergent ADA response
- The summary statistics (including number, median, Q1, Q3, minimum and maximum) of the peak post-baseline titer for patients with treatment-emergent ADA response
- Number (%) of patient with transient treatment-emergent ADA response
- Number (%) of patients with persistent treatment-emergent ADA response

- Number (%) of patients with indeterminate treatment-emergent ADA response
- Number (%) of patients with treatment-boosted ADA response
- The summary statistics (including number, median, Q1, Q3, minimum and maximum) of the peak post-baseline titer for patients with treatment-boosted ADA response , and patients with persistent, indeterminate and transient ADA response
- The summary statistics (including number, mean, SD, median, Q1, Q3, minimum and maximum) of the ratio of peak post-baseline titer to baseline titer for patients with treatment-boosted ADA response
- Number (%) of patients with ADA status (negative or positive in the ADA assay) at ADA time points analyzed
- Number (%) of patients with neutralizing antibody status (negative or positive in the neutralizing antibody assay) for the ADA positive patients at ADA time points analyzed
- The summary statistics (median, Q1, Q3, minimum and maximum) of ADA titers at ADA time points analyzed
- Listing of ADA peak titer levels and neutralizing antibody status at time points analyzed for patients positive in the ADA assay
- Number(%) of patients with neutralizing antibody status

Kinetics of treatment-emergent ADA positive response

Number (%) of patients with treatment-emergent ADA positive response at time points analyzed will be summarized by each treatment group.

Plot of percentage of patients with treatment-emergent ADA positive response at time points analyzed will be provided by each treatment group.

Impact of ADA on PK, clinical efficacy, and clinical safety

Associations between the PK, efficacy and safety endpoints and the following ADA categories will be explored:

- Treatment-emergent +treatment-boosted ADA response
- Pre-existing immunoreactivity + negative at all time points
- Treatment-emergent ADA response
- Persistent treatment-emergent ADA response
- Transient treatment-emergent ADA response
- Indeterminate treatment-emergent ADA response
- Treatment-boosted ADA response
- Pre-existing immunoreactivity
- Negative at all time points

- Neutralizing antibody positive
- Neutralizing antibody negative

Impact of ADA on PK

Associations between the ADA categories and serum concentration of dupilumab may be explored for the dupilumab dosed group. Plot of serum concentration of functional dupilumab by visit will be provided by the ADA categories for the dupilumab dosed group.

Impact of ADA on clinical efficacy

Associations between the ADA categories and the primary efficacy endpoint may be explored for the dupilumab dosed group by generating descriptive statistics of the endpoint (numbers of patients, means, and standard errors) by the ADA categories.

Impact of ADA on clinical safety

Associations between the ADA categories and safety may be explored by providing the number (n) and percentage (%) of patients with the following events by the ADA categories:

- Injection site reaction HLT
- Hypersensitivity reactions (medically reviewed)
- Anaphylactic reactions
- Overall incidence of severe TEAEs
- Overall incidence of serious TEAEs
- Overall incidence of TEAEs leading to permanent treatment discontinuation
- Additionally, the above events occurred on or after the first identified ADA-positive response after the first dose will be summarized for patients with treatment-emergent ADA.

2.4.6.2 Pharmacodynamic/genomic analyses

PD biomarkers will be analyzed in the safety population. Baseline values will be the last value collected prior to the first IMP.

For all parameters including antigen-specific IgEs with ≥ 0.35 kUA/L incidence of greater than 25% at baseline, levels at each visit, absolute changes from baseline and percent changes from baseline will be summarized in descriptive statistics (mean, SD, median, Q1, Q3, min, max) and plotted (mean +/- standard error of the mean) by treatment group and time point. For summarizing and plotting antigen-specific IgEs, only those individuals with a baseline value ≥ 0.35 kUA/L will be included in the calculation of descriptive statistics.

Values reported as below the LLQ (lower limit of quantitation) will be imputed as a value one half of the LLQ.

Number and percentage of patients with no ≥ 0.35 kUA/L antigen-specific IgE, with ≥ 0.35 kUA/L for only one antigen, and with ≥ 0.35 kUA/L for at least two antigens will be summarized by treatment group and time point. Same analysis will also be performed using LLQ as the threshold.

Additionally, descriptive statistics (including number, mean, SD, median, Q1, Q3, min, max) of biomarkers at baseline will be summarized for the ITT population. For randomized but not treated patients, baseline value will be the last value collected prior to the randomization.

For the PD endpoints collected only for subjects enrolled in selected sites in Canada, if the number of subjects with available data is small, then listings of the levels of the endpoints instead of the summary statistics will be provided.

Exploratory analysis of DNA/RNA will be addressed in a separate document.

2.4.7 Analyses of quality of life/health economics variables

Change from baseline in ACQ-5, AQLQ, EQ-5D-5L, SNOT-22, and HADS are analyzed as efficacy endpoints as described in Section 2.4.4.4.3.

Analyses of health care resource utilization will be performed under the responsibility of the Health Economics and Reimbursement Argumentation department of Sanofi. Methods and results will be made available in a separate report.

